This multi-method study will collect data from 100 African American patients (80 patients in stages 2, 3A, 3B, and 4 of CKD and 20 with no CKD diagnosis) utilizing both cross-sectional (aim 1) and experimental (aim 2) research designs (see Figure 1). The proposed methods were designed to maximize the robustness of the data while minimizing bias in study design, methodology, analysis, interpretation, and reporting. The use of validated instruments enhances the study's scientific rigor for aim 1. Random assignment to condition (for aim 2) eliminates selection bias as one potential threat to internal validity among others.²⁷ Additionally treating the two groups equivalently in terms of data collection methods and instrumentation improve internal validity by minimizing testing and instrumentation effects.²⁷ Detailed recruitment and data collection protocols further enhance the scientific rigor of the study because they ensure equal treatment of participants regardless of study condition. Finally, by intentionally studying patients along the continuum of CKD, we can explore whether there are "critical periods" in CKD progression where the relationships with stress are strongest.

Figure 1. Study Design

A. Organizational Structure

This study is funded by the National Institutes of Health (NIH), National Institute of Diabetes and Digestive and Kidney Diseases (NIDDK), and was developed by faculty in the Rollins School of Public Health. An internal medicine clinic within Emory University Hospital Midtown (at which Co-Investigator [name] currently serves as a practicing nephrologist) and the Georgia Clinical and Translational Science Alliance (GCTSA) (for which [name] serves as Co-Director) will serve as study sites. Additionally, study participants' bio-specimens will be analyzed at the Molecular Neuroimmunology Laboratory in the Department of Epidemiology at Emory. [name], who also serves as a Co-Investigator on this project, will oversee analyses of select blood samples. Outside laboratory resources will be used for processing and analyses of the remaining biospecimens.

B. Setting and location

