Study participation entails completion of a computer administered personal interview (CAPI) that assesses experiences of general and discriminatory stress, behavioral and socio-economic variables, and other psychological characteristics. Upon completion of the CAPI, participants would be scheduled to attend a second session. During this session the experimental manipulation entails them being asked to recall a general or discriminatory stressor (the participant is randomized to one of the two groups), while changes in blood pressure and inflammatory processes are monitored. Finally, participants provide blood pressure assessments over a 24-hour period using an ambulatory blood pressure monitor (ABPM). These methods are described below.

Data Collection Procedures

Day 1: Consent, CAPI and 24-hour Ambulatory Blood Pressure Monitor (ABPM)

Day 1 of data collection will occur at the Nephrology clinic within the Emory University Hospital, Midtown location. Those who consent to participate in the study will first complete a CAPI in a small private room at the clinic immediately following their appointment. This is a self-administered survey in which responses are directly entered into an iPad at the time of administration, thereby eliminating the need for subsequent data entry. REDCap software will be used to securely collect and manage CAPI-questionnaire data. The key advantages of this method include allowing the interviewer to answer respondent questions, probe for adequate

answers, and accurately follow complex instructions or skip patterns.³¹ The survey will assess participants' experiences of general and discriminatory stress, behavioral and socio-economic variables, and other psychological characteristics. Participants will be paid a portion of the monetary incentive (\$50) at the conclusion of the survey interview. The proposed CAPI-questionnaire is attached.

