Next, participants will undergo a moderate psychological stress adapted from the commonly used Trier Social Stress Test (TSST)³³. The TSST protocol has been adapted for use in recalling race-related experiences³⁴ underscoring its appropriateness for our protocol. [name] (Co-Investigator) and colleagues, have also used a similar experimental protocol and will provide related expertise for this project.^{35,36} Participants will be asked to recount one real-life stressful situations; one event will be a stressful race-related event and one event will be a stressful event that is not race-related. We will randomize participants such that half will recall the racial experience and half will recall the non-racialized stressful event. Each participant will have an equal chance of being placed in the racialized or non-racialized experience group. The Project Coordinator will provide instructions using a script. Participants will be given two minutes to prepare their statement, and three minutes to deliver the statement. There will be an 'audience' present at each participant's speaking task. Aligning with previously conducted involving audiences^{33,35-38}, each audience will include two observers who are of same race as the participant (African American), to heighten stress responses. Observers will wear white coats, and will be trained on the study protocol such that their behaviors are identical for each

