manipulation task. The audience will be trained to remain neutral during the task, told to not show empathy and not to smile at any time during the test. Observers have not yet been identified, however once determined, the individuals serving as observers will obtain a CITI certification, and study staff will submit observer credentialing as amendment modification to the protocol. The project coordinator will also remain in the room while participants recall each designated stressful experience. Blood pressure readings will be taken every 1 minute during the participant's preparation time and the actual recall task. The participant will be expected to use the entire three minutes for recall in each exercise; the project coordinator will cue the participant to continue until the 3-minute mark via standardized prompts from a script. Participants will be asked to rate their level of distress caused by the stressful event using an adapted version of Cooper's racism recall scale.³⁴ and again rate their level of distress on a linear scale (0 to 100) using the SUDS³². Participants will undergo a 45-minute recovery period after the first recall task; blood pressure readings will be taken every 5 minutes during this period. Immediately following the first 45-minutes of recovery, participants will provide a third blood draw (6 mL). Participants will undergo another 45-minutes of recovery, and provide and one final blood draw (6 mL) at the conclusion of the recovery period.

Over the course of the study, participants will provide 3, 4 mL samples of blood and 3, 6mL samples of blood. A total of up to 30 mL may be taken over the course of the study. The project coordinator will debrief participants on the purpose of the experimental manipulation and common reactions to it. Participants will also be debriefed on the entire experimental manipulation experience, including the audience's purpose. Participants will be paid \$150 at the conclusion of Day 2 (\$50 for return of ABPM and \$100 for completion of experimental manipulation). The experimental protocol along with data time points are outlined in Figure 2.

Data Sources

Participants will be asked to provide data from the following sources:

- **Cross-sectional survey data** that are provided by completing the CAPI (see attached)
- **Medical chart data**, used only to verify their last eGFR in order to achieve equal numbers of participants by study stage/CKD diagnosis

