We will start by creating a data set that merges the survey data with all biometric data. Traditional data entry for the survey data will be unnecessary as data will be imported directly into SPSS from the REDCap software that houses the CAPI-questionnaire. Data will be cleaned, coded, and examined for any missing data or unlikely values. We will examine frequency distributions for all variables, with particular attention to variable ranges, missing values, and transforming variables as needed, depending on evidence of internal consistency within scales. Next, we will conduct exploratory analyses to determine whether participants with the different sequences (i.e. race-related recall first or second) differ on demographic, clinical, or behavioral variables. Specifically, we will use logistic models to regress recall sequence on all relevant variables. If significant differences are identified, we will conduct further analyses by stratifying by these particular variables and consider adjustment for these variables in our main analyses as described below.

B. Main Outcome Analyses

These analyses are driven by the two hypotheses stated above: (1) Chronic discriminatory stressors will be associated with poor kidney functioning independent of other chronic stressors

as mediated by CKD-related inflammatory biomarkers and autonomic arousal; (2) Discriminatory stressors will be more physiologically impactful than general stressors on critical CKD-related inflammatory biomarkers and blood pressure reactivity.

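### The balance check models a recall order that no participant has; read as assigned arm, it lets chance baseline differences prompt stratified and possibly adjusted Aim 2 results

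*Combined protocol and SAP*

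**What the plan says.** Section VIII.A (Exploratory Analyses) sets out to "determine whether participants with the different sequences (i.e. race-related recall first or second) differ on demographic, clinical, or behavioral variables". The method follows: "Specifically, we will use logistic models to regress recall sequence on all relevant variables". If any difference is significant, "we will conduct further analyses by stratifying by these particular variables", and the team will "consider adjustment for these variables in our main analyses as described below". The paragraph gives no significance level, no list of variables and no rule for multiple tests.

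The design sections describe parallel groups. In the Data Collection Overview, "the participant is randomized to one of the two groups". Under Day 2 in Section III.E, "We will randomize participants such that half will recall the racial experience and half will recall the non-racialized stressful event". Items vii and viii of Research Instruments and Assessment, the Overall Time Burden paragraph and the 2×3 ANOVA in Section VIII.B are all consistent with one recall per person. Section III relies on the randomisation: "Random assignment to condition (for aim 2) eliminates selection bias as one potential threat to internal validity".

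The Day 2 text also keeps some two-recall wording. It asks for one situation but then describes two events, one racial and one not. It has the coordinator present "while participants recall each designated stressful experience", speaks of more than one exercise, and places the recovery period after a first task.

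**The concern.** There are two linked problems. First, the outcome of the logistic models is undefined, because order requires two recalls per participant.

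Second, the obvious repair, reading sequence as arm, leaves a significance test of baseline variables between randomised groups. Correct randomisation makes the null hypothesis true for every baseline variable, so a small p-value reports chance. It does not show that a variable predicts the outcome, which is the reason to adjust for one. The paragraph still gives the result consequences: stratified analyses are promised and adjustment is to be considered.

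Section VIII.C says the study exists to supply effect sizes for a later power calculation. Which stratified and adjusted Aim 2 estimates are produced should therefore not depend on chance flags.

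**Working it through.** **1. Is there a sequence?** Day 2 schedules one preparation, one recall and then 90 minutes of recovery. The blood volumes agree. The 4 mL samples are for A1C, creatinine and eGFR; the 6 mL samples for inflammatory markers come before the task and 45 and 90 minutes after it. That gives 3 × 4 + 3 × 6 = 30 mL, the stated maximum, with no samples left for a second recall. The two-recall phrases therefore look like left-over wording and do not define a second task.

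**2. How many variables would be tested?** The check covers demographic, clinical and behavioural variables. Item vi (Covariates) gives examples: 4 behavioural, 4 comorbidity and 3 demographic, so 4 + 4 + 3 = 11. Adding 3 socio-economic items gives 14, and 2 psychosocial items gives 16. These are only examples, so the true number k is open.

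**3. How often would chance raise a flag?** The documents give no figure to reproduce. Assumptions: .05 two-sided, 100 participants, 50 per arm, normally distributed covariates. For k independent separate tests, P(at least one flag) = 1 − 0.95^k. The remaining columns are from 4,000 simulated trials.

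| k | 1 − 0.95^k | Separate tests, independent | Separate tests, correlation .3 | Joint logistic, independent | Joint logistic, correlation .3 |
|---|---|---|---|---|---|
| 11 | 43.1% | 43.4% | 36.6% | 46.1% | 44.6% |
| 14 | 51.2% | 50.5% | 44.4% | 56.6% | 57.2% |
| 16 | 56.0% | 56.0% | 48.2% | 63.2% | 61.6% |

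The expected number of flags with separate tests is 0.05k, or 0.55 to 0.80. The joint model flags more often because 50 per arm over 16 coefficients is about 3 participants per coefficient, which makes its Wald tests somewhat anti-conservative.

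**4. Does the trigger inflate type I error?** In 10,000 simulated trials (k = 11 and 16, covariates explaining an assumed 10% or 30% of outcome variance), the unadjusted test rejected in .048–.052. Adjusting whenever a variable was flagged gave .041–.047. Reporting whichever of the two results was significant gave .055–.059.

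**5. What can a covariate do for precision?** Assume unit variance at each time point and within-person correlation .5, and compare adjusted with unadjusted analyses.

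- Between-subject main effect: a covariate correlated .5 with every time point cuts the 95% half-width from .323 to .257.
- Change score: residual variance is 2(1 − .5) − (r_task − r_rest)². If the two correlations are equal, nothing is gained (.396 to .398–.399). If they are .1 at rest and .5 at task, it is 1 − .16 = .84. The half-width becomes about .396 × √.84 = .363, against .365 simulated.

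A covariate therefore sharpens the change score if it predicts reactivity. Section VIII.A's test looks at association with arm, not with outcome or reactivity, so it cannot pick out such covariates.

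**The case against.** The section is labelled exploratory, adjustment is only to be considered, and Section VIII.C disclaims power for significance. The plan also does not rest on this check for its covariates: Day 2 promises control for medications and conditions, Data Sources treats body mass index as a standard control, and the ANOVA in Section VIII.B is adjusted anyway. All of this stands and keeps the impact modest. It does not remove the problem, because stratification after a flag is promised outright and no closed list is given for the Aim 2 model.

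A balance check might also be defended as a safeguard. The documents give no allocation method and do not say when randomisation occurs. If assignment came before Day 2, non-return or early termination could leave analysed groups that differ by more than chance. That is a fair limit: the chance-only statement applies to groups as randomised. But the plan does not present the check as a test of attrition, and a p-value against arm would still be a poor basis for choosing covariates.

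Two stronger readings are tempting. A reader might infer that the trigger inflates false positives. It does not when followed mechanically; the rise to about .06 needs selective reporting, which the plan does not propose. A reader might also infer that baseline covariates cannot help the change score or the condition-by-time contrast. That holds only if the covariate relates equally to every time point, which nothing in the documents establishes.

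**Conclusion.** The concern holds. The check cannot be run as written, because recall order does not exist in a one-recall design. Read as arm, it is a significance trigger on randomised groups. At an assumed .05 level with 11 to 16 variables, it would flag at least one in roughly 37% to 63% of correctly randomised trials, depending on the test and the correlation between variables. The level, the number of variables and the correlation are assumptions.

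The flag rate should not be read as the rate of changed conclusions, and the effect of the stratified analyses has not been quantified. The damage is to reproducibility: two analysts following the text could produce different stratified and adjusted Aim 2 estimates. It should be corrected, but it does not invalidate the randomised comparison.

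**What to change.** - Reconcile the Day 2 wording and Section VIII.A with the one-recall design, and replace recall sequence with assigned recall condition.
- Tabulate baseline variables by arm without significance tests.
- Delete the significance trigger for both stratification and adjustment.
- Adjust the Aim 2 model for a short list fixed in advance on prognostic grounds, for example the five-level CKD category already collected for the quotas. State how the medications, conditions and body mass index already promised as controls enter that model.

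The cost is wording, plus a small loss of power if the chosen covariates turn out to be uninformative. In 20,000 simulated two-arm trials (50 per arm, d = .5), four non-prognostic CKD-category terms lowered power from .70 to .68. Eleven useless continuous covariates lowered it from .69 to .64 and sixteen to .62, which is why the list should stay short.

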The first hypothesis is a meditational hypothesis. We recognize that Baron and Kenny⁶⁴ methods for testing mediation are among the most widely cited, but also acknowledge that there are convincing critiques of this approach such as the requirement that there be a significant direct effect of the independent variable on the outcome in order to proceed with meditational analyses.^{65,66} Thus, we will use meditational methods proposed by Zhao et al⁶⁵ that entail first running the Preacher and Hayes⁶⁷ SPSS syntax commands to generate “bootstrap” results for the indirect effect of chronic discriminatory stress (controlling for general stress) on each of the two kidney outcomes (eGFR and proteinuria) through the inflammatory pathway as measured by each of the proposed biomarkers (MCP-1, IL-6, suPAR). Bootstrapping relaxes assumptions about the shape of the sampling distribution of the indirect effect over repeated sampling from the population.⁶⁸ These analyses will control for relevant covariates. Next we will classify the type of mediation using the Zhao et al typology (complementary, competitive, indirect only, direct only, or non-mediation), and proceed with interpreting the findings in light of our hypotheses. We will consider using structural equation modeling as another technique recommended to test mediation.^{69,70}

The second hypothesis will entail use of a 2X3 ANOVA to simultaneously test the main effects of stress recall (race-related or not) (discriminatory stress vs. general stress) and data collection time point (rest, stress, and recovery) on each of the outcomes (i.e., each inflammatory biomarker and blood pressure), also controlling for the relevant covariates. This test provides a form of economy by examining multiple effects at a time, while also allowing us to study the interaction between study condition and time.⁷¹

C. Statistical Power

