The proposed proof-of-concept study is designed to generate effect sizes to inform a future power analysis and thereby establish the legitimacy of studying this topic in a subsequent large-scale clinical trial. Thus, it is not intended to achieve the level of power to demonstrate statistical significance as is common in larger studies. Nevertheless, regarding study aim 1, if we were to perform a multiple regression with 8 predictors that explain just 15% of the variance in a given outcome, we would achieve 84% power at $\alpha=.05$ (<http://danielsoper.com/statcalc3/calc.aspx?id=9>) at N=100. For aim 2, collecting data at multiple time points is one way to maximize power. If we just consider the two study groups (intervention and control) we would achieve power of .80 to detect a medium effect (.25) at $\alpha=.05$ with a sample of just 64 participants.⁷²

IX. Training of study team

All research staff maintains a current CITI, (Group 3 Social/Behavioral) certification. Proof of certifications has been uploaded for further review. Corresponding study team members (including members of the Georgia CTSA team and nurses within the Emory University Healthcare Nephrology clinic) will undergo study-specific training.

X. Plans for monitoring the study for safety

The Data and Safety Monitoring Plan (DSMP) outlined below will adhere to the protocol approved by Emory University. An IRB-approved written informed consent will be obtained from each participant at entry into the study; elements of informed consent will include: (a) having the participant review the study consent form; (b) having the investigator(s) or study staff meet with the participant to review the consent, confirm understanding, and answer any questions; and (c) once the investigator(s) or study staff are convinced that the protocol is understood and that there is agreement to participate, having the consent signed. The principal investigator (PI) will review all data collection documents weekly for completeness and accuracy of the data as well as protocol compliance. The PI will review this protocol on a continuing basis for participant safety and include the results of the review in annual progress reports submitted to the IRB and the NIH.

Patient Monitoring will be performed by the P.I., Co-Investigators, the Project Coordinator and medical staff present during the experimental manipulation. Also, H&P is required per the GCTSA protocol.

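### Three of the five mediation labels declare a path absent in a study not powered to show it; at N=100, if all paths are real and sized 0.2 to 0.3, roughly 35-90% of labels are wrong

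*Combined protocol and SAP*

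**What the plan says.** Section VIII.B (Main Outcome Analyses) plans bootstrapping that yields "results for the indirect effect of chronic discriminatory stress (controlling for general stress) on each of the two kidney outcomes (eGFR and proteinuria"). Each inflammatory marker is to serve as a mediator in its own right: MCP-1, IL-6 and suPAR. Two outcomes and three biomarkers make 2 × 3 = 6 pairs. The next step is to "classify the type of mediation using the Zhao et al typology (complementary, competitive, indirect only, direct only, or non-mediation"), and then to "proceed with interpreting the findings in light of our hypotheses".

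The section gives no interval level, no test for the direct path, no criterion for calling a path absent, and no instruction to show path estimates with intervals beside the label.

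Section VIII.C (Statistical Power) sets the purpose: "The proposed proof-of-concept study is designed to generate effect sizes to inform a future power analysis". It adds that "it is not intended to achieve the level of power to demonstrate statistical significance as is common in larger studies". Its only aim 1 power figure is 84% at alpha .05 and N=100, for "a multiple regression with 8 predictors that explain just 15% of the variance in a given outcome".

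**The concern.** *Indirect only* says there is no direct path, *direct only* says there is no indirect path, and *non-mediation* says there is neither. If the basis for saying so is an interval or test that fails to exclude zero, the label depends on precision as much as on biology. A study that disclaims power for significance cannot treat non-significance as absence.

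The results are meant to inform a larger prospective study. A real direct effect missed for lack of power would appear as *indirect only*, which invites a reading of full mediation. A real indirect effect that was missed would appear as *direct only* or *non-mediation*, and the biomarker could be dropped from the next study because of this study's sample size.

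**Working it through.** **Inputs from the documents.** N=100 (Section II); 8 predictors, R² = 0.15, alpha .05 and 84% power (Section VIII.C); 2 outcomes and 3 biomarkers (Section VIII.B).

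**Assumed, because the documents give none.** Standardised path sizes: a (exposure to biomarker), b (biomarker to outcome) and c' (direct). Also assumed is the labelling rule: a path is present if its 95% interval or .05 test excludes zero.

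**Step 1: reproduce the 84%.** f² = 0.15/0.85 = 0.1765; λ = 100 × 0.1765 = 17.65; noncentral F on 8 and 91 df gives 83.6%. The figure reproduces, as an omnibus test of all eight predictors together.

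**Step 2: power for one coefficient** in the same model (1 and 91 df, λ = 100·r²/(1−r²)).
- Partial r = 0.14: λ = 100 × 0.0196/0.9804 = 2.00, power 29%.
- Partial r = 0.20: λ = 100 × 0.04/0.96 = 4.17, power 52%.
- Partial r = 0.30: λ = 100 × 0.09/0.91 = 9.89, power 88%.
- The 15% spread evenly over 8 predictors: λ = 100 × 0.01875/0.85 = 2.21, power 31%.

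**Step 3: simulate the labels.** Each setting used 1000 data sets with N=100, an exposure, one mediator and six unrelated covariates. M = aX + error and Y = bM + c'X + error, all with unit variance. The indirect effect counts as present if the 95% percentile bootstrap interval for ab (1000 resamples) excludes zero; the direct effect counts as present if p < .05. The true label in every row is *complementary*. Entries are percentages, with Monte Carlo error of about ±3 points.

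| a, b, c' | complementary (right) | indirect only | direct only | non-mediation | wrong |
|---|---|---|---|---|---|
| 0.2, 0.2, 0.2 | 10.5 | 15.3 | 37.7 | 36.5 | 89.5 |
| 0.3, 0.3, 0.2 | 35.8 | 37.0 | 16.5 | 10.7 | 64.2 |
| 0.3, 0.3, 0.3 | 65.2 | 9.6 | 22.5 | 2.7 | 34.8 |
| 0.39, 0.39, 0.3 | 85.6 | 11.2 | 3.0 | 0.2 | 14.4 |
| 0.5, 0.5, 0.3 | 92.5 | 7.5 | 0 | 0 | 7.5 |

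Two repeat simulations gave 10% and 11% right for the first row, 39% and 38% for the second, and 64% and 68% for the third.

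**Step 4: hold R² at the plan's own 0.15.**
- If exposure and biomarker share all of it equally, b = c' = √(0.15/(2+2a)). For a = 0.3 this is √(0.15/2.6) = 0.24, and the labels fall as 34% *complementary*, 32% *direct only*, 23% *indirect only* and 11% *non-mediation*. Over a = 0.14 to 0.5, 66-86% are wrong.
- If the 15% is spread evenly over eight predictors (b = c' of 0.14 to 0.16), the right label appears in only 2.4-4.5% of studies.

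**Step 5: cases where a path really is absent.**
- No effects at all: *non-mediation* is right 96% of the time.
- c' = 0 and the biomarker carries all 15% (b = √0.15 = 0.39): *indirect only* is right 50%, 77% and 90% of the time for a = 0.2, 0.3 and 0.39.

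**Step 6: sample size for reliable labels.** With a = b = c' = 0.2, 79% of labels are right at N=300 and 94% at N=400 (500 data sets each).

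**The case against.** The strongest reply is that the plan never says a non-significant path is absent. It names a typology from a cited source and stops there, so the rule tested above is a reading of the text. That is fair, and the rule is marked as an assumption. It follows from the label names, the bootstrap step and the only alpha given (.05). No other basis for declaring absence is offered.

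Second, the study is openly a proof of concept, effect sizes are its product, and it is the findings that are to be interpreted in light of the hypotheses. A reader might infer that the aim 1 conclusion will rest on the labels alone. The documents do not say that, and nothing in them stops estimates being reported alongside. What stands is that nothing in Section VIII.B requires it, while the classification is required.

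Third, the size of the error depends on assumed paths with the truth fixed as *complementary*. A reader might take 35-90% as a general mislabelling rate. The documents give no path sizes, and Steps 3 and 5 show much lower error for large paths and when there are no effects.

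Fourth, a reader might suppose that covariate adjustment makes matters worse. The calculations do not show it: with six unrelated covariates the error was 90% (paths of 0.2) and 35% (paths of 0.3), against 90% and 36% without covariates.

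The 84% power figure is no rebuttal, because the labels rest on single paths.

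**Conclusion.** The concern holds in a conditional form. Section VIII.B commits to labels of which three assert absence, and Section VIII.C disclaims the power that would be needed to support them. If all paths exist at standardised sizes of about 0.2 to 0.3, a given pair is mislabelled in roughly 35-90% of studies at N=100. Within the plan's own R² of 0.15, shared equally by exposure and biomarker, the range is 66-86%. For large paths it is about 8-14%. The investigators will not know which case applies, and the label alone will not tell the reader.

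These figures rest on the inferred significance rule, normal data, covariates unrelated to the paths, no missing values and one mediator at a time. They are per label; the chance that all six labels are right was not calculated.

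**What to change.** In Section VIII.B, replace the classification sentence with wording to this effect:

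> For each biomarker and kidney outcome, a, b, the indirect effect ab, the direct effect c' and the total effect will be reported on a standardised scale with 95% intervals, as the main aim 1 result. A path whose interval includes zero will be described as not resolved. Typology labels, if given, are descriptive only and appear beside the intervals; a non-significant path has not been shown to be absent.

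A common equivalence margin such as ±0.1 should not be used to license the absence labels. Indirect effects are products: 0.2 × 0.2 = 0.04 and 0.3 × 0.3 = 0.09 both lie inside it. In simulation at N=100 with a = b = c' = 0.2, the interval for ab fell inside ±0.1 in 49% of studies, and a false *direct only* was still given in 28% (42% with c' = 0.3). The direct-effect interval, with a half-width of about 0.19 to 0.20, never fitted inside it.

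The cost is SAP wording. The estimates come from the bootstrap and regressions already planned, with no new data, visits or participants. The downside is that the report makes fewer categorical claims.
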